9.2.11 Frequency of Lubricant Application and Sexual Activity

These will be recorded daily in an electronic diary (eDiary). The number of days using lubricant and having intercourses will be summarized by using the number of non-missing observations, arithmetic mean, SD, and median by week for each treatment. They will be compared among each treatment group using Welch's t-test. And the mean

values derived from data in each week will be compared using the Welch's t-test. In the summarization, subjects with no record over half days during each week will be excluded.

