6.4 Missing Data

If numerical values are missing but characteristic values are not missing because some signs, namely < and >, are included in the characteristic values, the numerical values will be imputed following the below rules:

- If '<' is included in the characteristic value, a smaller value between the value without < or the lower range value will be imputed,
- If '>' is included in the characteristic value, a greater value between the value without > or the upper range will be imputed.

If the information of year or month is missing for duration of VVA, 0 will be imputed for calculating summary statistics but kept missing for listings.

Other missing data will not be imputed. All analyses will be based on observed data.

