	Week 8	ITT	ANCOVA	Treatment, Baseline	Secondary analysis
Change from baseline (Randomization) in bone marker	Week 12	ITT	ANCOVA	Treatment, Baseline	Secondary analysis
	Week 4	ITT	ANCOVA	Treatment, Baseline	Secondary analysis
	Week 8	ITT	ANCOVA	Treatment, Baseline	Secondary analysis
Frequency of lubricant application and sexual activity	Weekly	ITT	Welch's t-test	---	Secondary analysis
	Overall	ITT	MIMRM	Treatment, Week, Treatment*week	Secondary analysis
Overall satisfaction with treatment	Weekly	ITT	Wilcoxon rank-sum test	---	Secondary analysis

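### Weekly lubricant and intercourse counts are not adjusted for unrecorded diary days, and SAP 9.2.11 and Table 5 name different tests for the comparison across weeks

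*SAP*

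**What the plan says.** Women enter lubricant use and intercourse in the eDiary every day (Protocol 7.4). SAP 9.2.11 turns these entries into a weekly count: "The number of days using lubricant and having intercourses will be summarized" by week and treatment. Table 2 in SAP 6.3 makes each diary week seven days long.

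The only rule for incomplete weeks is "In the summarization, subjects with no record over half days during each week will be excluded". SAP 6.4 adds the general rule: "Other missing data will not be imputed. All analyses will be based on observed data". No section divides the count by the days recorded, scales it to seven days or adjusts for completeness.

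On testing, SAP 9.2.11 says of the weekly counts: "They will be compared among each treatment group using Welch's t-test". It then adds a second comparison, of mean values: "values derived from data in each week will be compared using the Welch's t-test". In Table 5 (SAP 9.4), the entry "Frequency of lubricant application and sexual activity" has two rows. The Weekly row gives Welch's t-test. The Overall row gives a repeated-measures model with treatment, week and their interaction. SAP 9.4 presents Table 5 as covering every inferential efficacy analysis. SAP 13, on changes from the protocol, does not address the difference.

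**The concern.** A count taken over four recorded days is not comparable with one taken over seven, yet both enter the same mean. A day without an entry adds nothing to the count, which has the same effect as recording no use. Elsewhere the SAP handles incomplete sums explicitly: for the VHI, VuHI, imaging, FSFI and UDI-6 totals, a missing component makes the total missing (SAP 9.2.5 to 9.2.9). Here a partial sum appears to be analysed as if complete.

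The sponsor's lubricant is supplied for use as needed against dryness (Protocol 3.2), so its use is context for reading the dryness co-primary endpoint. If one arm fills in the diary less fully, that arm would seem to use less lubricant or to have less intercourse. The two overall tests can also give different p-values for the same comparison, and the plan does not say which one governs.

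**Working it through.** The documents give no expected use, variability, completion rate or power for this endpoint, so there is no planned figure to reproduce.

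**Inputs from the documents.** Seven-day diary week (SAP 6.3, Table 2); exclusion when more than half the days have no record (SAP 9.2.11); two-sided 0.05 tests (SAP 6.2); about 300 women per arm (SAP 4.3).

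**Assumed inputs.** True use of 1, 2 or 3 days per week, equal in both arms; the daily completion rates shown below; a beta-binomial spread of use between women.

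1. *Weeks kept.* Half of 7 is 3.5, so 4 or more missing days exclude the week and 0 to 3 missing days keep it. Retained weeks have k = 4, 5, 6 or 7 recorded days.

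2. *Expected raw count* = true days × k/7, at a constant daily rate.

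| Recorded days k | Fraction of true count | A true 3 days is counted as |
|---|---|---|
| 4 | 4/7 = 57% | 1.71 |
| 5 | 5/7 = 71% | 2.14 |
| 6 | 6/7 = 86% | 2.57 |
| 7 | 100% | 3.00 |

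The largest shortfall in a retained week is 3/7 = 43%.

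3. *Arm difference with no treatment effect.* Suppose each day is recorded with probability 0.95 in one arm and 0.85 in the other. Among retained weeks the mean number of recorded days is 6.65 and 5.99. The raw means then differ by (true days/7) × 0.66, which is about 0.10, 0.19 and 0.28 days per week for true use of 1, 2 and 3 days. With 0.95 in both arms the difference is zero and both means are 95% of the truth (6.65/7).

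4. *False-positive rate of Welch's t-test.* Simulation with no true effect, 300 per arm, one week, 4,000 runs, weeks with k ≥ 4 kept:

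| Completion by arm | Raw count, true use 1 / 2 / 3 days | 7 × count/k |
|---|---|---|
| 95% and 95% | 0.044 / 0.048 / 0.047 | near 0.05 |
| 95% and 85% | 0.13 / 0.22 / 0.36 | near 0.05 |
| 90% and 75% | 0.20 / 0.39 / 0.61 | near 0.05 |

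The scaled count stayed between 0.044 and 0.059 throughout. The simulation drops days at random within the week, which is the condition under which scaling works.

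5. *The two statements of the overall test.* The by-week comparison is already covered when SAP 9.2.11 introduces the Welch test on mean values, so that second sentence most naturally describes the comparison across weeks. Table 5 gives a model for that comparison instead. The model appears nowhere in the text of 9.2.11, and Table 5 does not say which contrast gives the overall treatment effect.

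**The case against.** The SAP never says that an unrecorded day counts as no use. That is an inference from analysing a number of days without a denominator. SAP 6.4 rules out imputation, and the reference to mean values derived from each week's data could mean a mean over recorded days, close to the rate proposed here. This stands as a caution. The raw count remains the natural reading, and on either reading the scoring of a partial week needs to be stated.

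The plan also limits the problem. The worst weeks are dropped, not deflated; eDiary compliance is checked at Visits 3, 4 and 5; and the trial is double-blind with matching placebo, so nothing in the documents points to unequal completion.

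Scaling has its own weakness. If women skip the diary on days with nothing to report, the raw count is closer to the truth and scaling turns 4 of 4 into 7.

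On the tests, SAP 9.2.11 does not use the word overall, and Table 5 was damaged in extraction. But the terms in the Overall row (treatment, week and interaction, without center or baseline) match no other row, so misplaced text does not explain the mismatch.

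A reader might infer more than the documents support:

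- *That the analysis has a high false-positive rate.* Assume true use of 3 days, SD 2, 270 per arm, and 6 against 5 recorded days. The difference is 3/7 = 0.43, z = 0.43/(2 × √(2/270)) = 2.49, and the rejection rate is about 70%. At 6.5 against 6 recorded days it is about 24%. The arithmetic is right, but these inputs are assumed and the result comes from the assumed gap between arms.
- *That the diary is the trial's only record of background relief.* Prescription and OTC medications are also recorded (Protocol 6.2), and lubricants or moisturizers not supplied by the sponsor are prohibited (Protocol 6.2.1).
- *That the choice of test is left until after unblinding.* Both tests are written into the SAP, which is to be final before the blind is broken (Protocol 9.1). The gap is that neither is given precedence.
- *That a mean over weeks wrongly gives equal weight to women with few and many diary weeks.* One equally weighted summary per woman is a legitimate choice.

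**Conclusion.** The point holds as a minor one, in two parts. First, on the natural reading, retained weeks with 4, 5 or 6 recorded days are undercounted to 57%, 71% or 86% of the true value, assuming a constant daily rate. With equal completion by arm this is attenuation only, and the type I error stays near 0.05. With unequal completion it produces a spurious arm difference, whose size cannot be fixed from the documents. Second, the text and Table 5 name different methods for the comparison across weeks; this rests on reading the second Welch sentence as that comparison.

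These diary endpoints are among neither the protocol's objectives (Protocol 2.1 and 2.2) nor its listed secondary endpoints (Protocol 9.10.2), and no primary conclusion depends on them.

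**What to change.** In SAP 9.2.11, define the weekly value as 7 × days used / days recorded for each retained week. State that a week needs at least 4 recorded days and that the exclusion applies to that week only. Keep the raw count as a sensitivity analysis, because the scaled value assumes that unrecorded days resemble recorded ones. Tabulating recorded days per week by arm would show whether completion differed.

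Name one method for the overall comparison in both SAP 9.2.11 and Table 5. If it is the repeated-measures model, state the contrast, for example the treatment difference averaged over weeks, and remove the Welch test on the mean of weekly values.

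The cost is a few lines of SAP text and a small programming change. No new data are needed.

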9.2.12 Overall Satisfaction With Treatment

This will be recorded in an eDiary and summarized for each treatment group by week. The percentage of each category will be compared among each treatment group using Wilcoxon rank-sum test.

9.3 Secondary Endpoints That Will Be Summarized Descriptively Only, With No Inferential Analysis

9.3.1 Serum Hormone Levels

Estradiol (E2), luteinizing hormone (LH), sex hormone-binding globulin (SHBG), free testosterone, and total testosterone values will be summarized at baseline, Week 12 for each treatment group. Change from baseline to Week 12 will also be summarized. Basically, observation at randomization will be used as baseline.

	Week 8	ITT	ANCOVA	Treatment, Baseline	Secondary analysis
Change from baseline (Randomization) in bone marker	Week 12	ITT	ANCOVA	Treatment, Baseline	Secondary analysis
	Week 4	ITT	ANCOVA	Treatment, Baseline	Secondary analysis
	Week 8	ITT	ANCOVA	Treatment, Baseline	Secondary analysis
Frequency of lubricant application and sexual activity	Weekly	ITT	Welch's t-test	---	Secondary analysis
	Overall	ITT	MIMRM	Treatment, Week, Treatment*week	Secondary analysis
Overall satisfaction with treatment	Weekly	ITT	Wilcoxon rank-sum test	---	Secondary analysis

10 SAFETY

Safety analyses will be conducted on the Safety Population. For all safety analyses, emphasis will be on characterizing the changes from baseline and flagging clinically relevant abnormal findings, if feasible. If a test or assessment is measured more than once prior to the first dose of study medication, the baseline measurement is the last non-missing value that is observed prior to the first dose of study medication.

To calculate 95% confidence intervals for differences in incidence proportions, FREQ procedure and RISKDIFF option will be used.

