10.1 Adverse Events

All adverse events (AEs) will be collected from the time of informed consent through 14 days after the last dose of study medication. All AEs will be classified by SOC and PT using MedDRA Version 18.0 and presented in subject listings.

AEs that occurred from the first dose of study medication up to 14 days after the last dose will be considered treatment-emergent AEs (TEAEs). Only TEAEs will be counted in the summary tables described below. If more than one AEs that map to the same SOC or the same PT are occurred in a subject, the subject will be counted only once at each level of summarization (i.e., SOC level or PT level) using AE with the strongest outcome and/or severity.

If partial dates of onset are missing, the following imputation algorithm will be applied;

- If the information of period of onset is 'After first dose of study drug' and the month of onset is same as the first dosing date but day is unknown, the day will be same as the first dosing date.
- If the information of period of onset is 'After first dose of study drug' and the month of onset is different from the first dosing date but day is unknown, the day will be first day of the month.

All AEs will be listed. TEAEs will be summarized as assessments of short term safety and long term safety, separately. For assessment of short term safety, following TEAEs will be included;

- if a subject takes study medication for more than 12 weeks (beyond Visit 5), AEs that occurred until Visit 5 will be summarized;
- if a subject takes study medication for 12 weeks or less than 12 weeks, all TEAEs will be summarized.

For assessment of long term safety, the target safety population will be limited to subjects who continue to Part B in two previous protocols (original protocol:06Oct2012 and protocol amendment 1: 11Mar2016) and take study drugs more than 12 weeks (beyond Visit 5) and TEAEs after 12 weeks (beyond Visit 5) will be summarized.

The following summary tables of TEAEs will be produced:

1) Overview of Adverse Events

For each treatment group, the number of events and subjects who experience

- TEAEs
- Serious TEAEs
- TEAEs leading to withdrawal
- TEAEs with an outcome of deaths

will be counted and the incidence proportion will be calculated for each treatment group. The difference in the incidence proportion and its 95% confidence interval (CI) will also be calculated. Treatment-related AEs will be summarized by the same category as TEAEs, except for death.

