2) Summary of TEAEs and Treatment-related AEs by System Organ Class and Preferred Term

For each treatment group, the number and percentage of subjects who experience TEAE (and Treatment-related AEs) will be counted by SOC and PT for assessments of short and long term safety. The difference in the percentage and its 95% CI will also be calculated. For assessment of short term safety, This analysis will be performed for specific TEAEs for assessment of short term safety, namely

- Breast-related TEAE
- Reproductive system-related TEAE
- Lipid-related TEAE
- Coagulation-related TEAE
- Chemistry-related TEAE

TEAEs and Treatment-related AEs at least 2% in any treatment groups will be analyzed in a similar way.

3) Summary of Serious TEAEs and TEAEs Leading to Withdrawal by System Organ Class and Preferred Term

For each treatment group, the number and percentage of subjects who experience serious TEAE and TEAE leading to withdrawal will be counted by SOC and PT for assessment of short term safety. The difference in the percentage and its 95% CI will also be calculated.

4) Summary of TEAEs and Treatment-related AEs by System Organ Class by Maximum Severity and Outcome

For each treatment group, the number and percentage of subjects who experience TEAE (and treatment-related AEs) will be counted by SOC and PT, and by maximum

severity and outcome for assessment of short term safety. The order of severity and outcome are shown in Table 6.

Table 6 Order of Priority for Counting Number of Subjects

Order of Priority	Severity	Outcome
1	Severe	Fatal
2	Moderate	Recovered/Resolved with sequelae
3	Mild	Not recovered/Not resolved
4		Recovering/Resolving
5		Recovered/Resolved
6		Unknown

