10.3 Laboratory Evaluations

Safety laboratory tests shown in Table 7 will be conducted at screening, randomization, Week 12, and early termination before Visit 5 (hereafter ET).

Table 7 Safety Laboratory Tests

Category	Evaluation Items
Hematology Tests	hematocrit, hemoglobin, platelet count, red blood cell (RBC) count, white blood cell (WBC) count with differential (eosinophil count, basophil count, neutrophil count, monocyte count, lymphocyte count), platelet count, mean corpuscular hemoglobin (MCH), mean corpuscular hemoglobin concentration (MCHC), mean corpuscular volume (MCV), RBC distribution width (RDW), mean platelet volume (MPV)
Blood Chemistry Tests	ALP, ALT, AST, total bilirubin, GGT, LDH, BUN, creatinine, uric acid, sodium (Na), potassium (K), chloride (Cl), calcium (Ca), glucose, total protein
Lipids	Total cholesterol, low-density lipoprotein (LDL) cholesterol, very-low-density lipoprotein (VLDL) cholesterol, high-density lipoprotein (HDL) cholesterol, and triglycerides
Coagulation	Thromboplastin time, fibrinogen, antithrombin III, , protein-C, and protein-S
Urinalysis for Quantitative	pH, specific gravity
Urinalysis for Qualitative	Color, bilirubin, glucose, ketones, nitrite, occult blood, protein, microscopic evaluation of sediment, and urobilinogen

ALT = alanine aminotransferase; AST = aspartate aminotransferase; ALP = alkaline phosphatase; GGT = gamma-glutamyl transferase; LDH, lactate dehydrogenase; BUN, blood urea nitrogen

The measurements on safety laboratory evaluations will be handled as follows:

- 1) For quantitative scale items, summary statistics of measurements taken at baseline, Week 12 will be calculated by treatment group. The change from baseline to Week 12 will be also calculated by treatment group.
- 2) For qualitative scale items, frequencies for each category at baseline, Week 12 will be counted by treatment group.
- 3) For all laboratory analytes in Appendix 3, proportion of subjects who meet the predefined limits at any timepoints will be calculated. Difference in the incidence proportion among treatments and its 95% CI will be calculated. This analysis will be performed using data until Visit 5. The analysis will be applied to data taken at the last timepoint before stopping dosing until Visit 5.

The factor V Leiden will not be summarized.

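### SAP 10 names RISKDIFF but no interval type for safety incidence differences; if it runs as Wald, the upper limit in sparse rows falls well below the score-type limit

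*SAP*

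**What the plan says.** SAP 10 sets one rule for every safety incidence difference: "To calculate 95% confidence intervals for differences in incidence proportions, FREQ procedure and RISKDIFF option will be used". It gives a procedure and an option, but no interval type, continuity correction or rule for zero cells.

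The rule reaches these outputs:

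- **Adverse event overview** (SAP 10.1, item 1), which includes serious events, withdrawals and deaths: "The difference in the incidence proportion and its 95% confidence interval (CI) will also be calculated".
- **SOC/PT tables** (item 2), where events "will be counted by SOC and PT for assessments of short and long term safety".
- **Serious events and withdrawals by SOC/PT** (item 3), where "serious TEAE and TEAE leading to withdrawal will be counted by SOC and PT for assessment of short term safety". Items 2 and 3 both add: "The difference in the percentage and its 95% CI will also be calculated".
- **Appendix 3 laboratory limits** (SAP 10.3): "Difference in the incidence proportion among treatments and its 95% CI will be calculated". The data are cut: "This analysis will be performed using data until Visit 5".

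The 2% frequency rule in item 2 defines an additional table. It does not remove rare terms from the main one, so sparse rows do receive the interval.

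Protocol 9.11.1 had planned Clopper-Pearson intervals per arm. SAP 13.1 replaces them with intervals for the difference, and gives a reason. SAP 6.1 sets only a minimum SAS version. SAP 1 refers to a separate mock-up document, which was not available for this review.

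**The concern.** RISKDIFF can return more than one kind of interval, so two programmers following SAP 10 could report different limits from the same counts. If no type is requested and Wald results, sparse rows are where it matters. Wald estimates each arm's variance from its observed proportion. An arm with no events contributes zero variance, and an arm with one or two events contributes a variance that is small and itself poorly estimated.

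For a harm seen once or twice, the upper limit tells the reader how large an excess on ospemifene the data still allow. A limit that is too low understates that excess, and a 0 v 0 row printed with zero width claims a certainty that 300 women per arm cannot give. With the Clopper-Pearson intervals gone, the difference interval is the only planned interval on adverse event incidence.

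**Working it through.** **Inputs.** About 300 per arm, 1:1 (Protocol 9.2, SAP 4.3); 95% two-sided, z = 1.96. The documents give no adverse event rates, so all event counts and true rates below are assumptions. The plan states no figure for these intervals. Its one checkable design figure, at least 90% power with 300 per arm, reproduces: about 91% for the dryness effect size of 0.27.

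**Formulas**, with d = x1/n − x2/n (ospemifene minus placebo):

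- Wald: d ± 1.96 × √[p1(1−p1)/n + p2(1−p2)/n], using observed proportions.
- MN: the values δ at which (d − δ) / √{[q1(1−q1)/n + q2(1−q2)/n] × N/(N−1)} = ±1.96. Here q1 and q2 are the maximum-likelihood rates under q1 − q2 = δ, and N = 600.

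**Worked case, 1 v 0.**

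- Wald: d = 0.333%. The standard error is √[(1/300)(299/300)/300] = 0.333%, so the upper limit is 0.333 + 0.652 = 0.99%.
- MN: at the upper limit q2 = 0 and q1 = δ, so (δ − 1/300)² = 3.8415 × δ(1−δ)/299.5. This gives δ = 1.87%.

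**Worked case, 0 v 0.** Wald gives (0, 0). MN gives δ = 3.8415/(3.8415 + 299.5) = 1.27%, so ±1.27%.

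**Upper limits at 300 per arm**

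| Events | Wald | MN | Wald shorter by |
|---|---|---|---|
| 1 v 0 | 0.99% | 1.87% | 47% |
| 2 v 0 | 1.59% | 2.40% | 34% |
| 3 v 0 | 2.13% | 2.90% | 27% |
| 2 v 1 | 1.46% | 2.10% | 30% |
| 6 v 3 | 2.94% | 3.42% | 14% |

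**Coverage when ospemifene has the higher rate.** Both binomials were enumerated exactly, given at least one event. Results are averaged over assumed ospemifene rates of 0.4% to 2.0% in steps of 0.05 points, always above placebo.

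| Placebo rate | Wald upper miss | Wald lower miss | Wald coverage | MN upper miss | MN lower miss | MN coverage |
|---|---|---|---|---|---|---|
| 0 | 5.79% | 0.37% | 93.8% | 0.15% | 2.73% | 97.1% |
| 0.1% | 6.38% | 0.45% | 93.2% | 0.50% | 2.81% | 96.7% |
| 0.2% | 6.03% | 0.56% | 93.4% | 0.78% | 2.90% | 96.3% |
| 0.5% | 4.51% | 1.01% | 94.5% | 1.43% | 2.97% | 95.6% |

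Nominal is 2.5% on each side. At single grid points the Wald upper miss runs from 0% to 15.6%.

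**Equal rates.** At 0.3%, 0.5% and 1% in both arms, over all tables, two-sided coverage is 98.92%, 97.04% and 95.36%, the same for Wald and MN. Halving the remainder gives upper misses of 0.5%, 1.5% and 2.3%, none above nominal.

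**Excess on placebo.** Swapping the arms swaps the two miss columns, so Wald upper misses average 0.37% to 1.01%. The shortfall moves to the lower limit.

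**The case against.** - **The documents do not say Wald.** A reader might infer that the SAP has chosen it. It has not: the link from an unqualified RISKDIFF call to Wald is an assumption about the software, and the mock-ups may name another type. This stands. What holds regardless is that SAP 10 names no type.
- **Too low is conditional.** A reader might infer that the limit is too low in every row with 0 to 3 events. Undercoverage at the upper limit needs a true excess on ospemifene; equal rates or an excess on placebo do not produce it.
- **The averages depend on the grid.** No rate in the documents supports 0.4% to 2.0%. With placebo at 0.1%, the Wald upper miss is only 1.4% at an ospemifene rate of 0.4% and 1.9% at 1.0%. Between 46% and 74% of the grid's probability lies in tables with more than 3 events. So 4.5-6.4% is an illustration, not the miss rate of sparse rows.
- **Part of the gap is MN's own conservatism.** Against a mid-P upper limit for the ospemifene arm alone (1.63%, 2.18% and 2.70% for 1, 2 and 3 v 0), Wald is short by 40%, 27% and 21%. The gap shrinks but does not disappear.
- **0 v 0 is a narrow case.** An SOC/PT table would not normally list a term that nobody reported. Zero width matters mainly for fixed rows, in the overview and the laboratory limits.
- **Nothing is decided on these intervals.** The tables are descriptive, counts per arm are shown and all adverse events are listed. This stands, and it sets the severity.

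**Conclusion.** The point holds as a minor specification gap with a cheap improvement available. SAP 10 leaves the interval type open for every safety incidence difference. If the call yields Wald, the upper limit at 300 per arm is 27% to 47% below the MN limit for 1 to 3 v 0, fading to 14% at 6 v 3, and fixed 0 v 0 rows get zero width. Where ospemifene truly has the higher rate, upper misses average 4.5-6.4% on the assumed grid, while two-sided coverage stays at 93.2-94.5%. Confidence is medium, because the numerical part rests on the Wald assumption and on assumed rates.

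Three stronger readings are not supported:

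- **That safety conclusions would be wrong.** There is no decision rule, and no efficacy result is touched.
- **That dropping Clopper-Pearson was an undisclosed departure.** SAP 13.1 discloses and explains it, as Protocol 9.1 allows.
- **That the smaller Part B subset worsens every table.** SAP 10.1 does say "For assessment of long term safety, the target safety population will be limited to subjects who continue to Part B", but the serious and withdrawal SOC/PT tables are short term only and the laboratory limits stop at Visit 5. The subset can affect only the long-term SOC/PT rows and possibly the overview. Its size is not given. At an assumed 100 or 50 per arm, the 1 v 0 upper limit would be 2.95% against 5.47%, or 5.88% against 10.56% (Wald against MN).

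**What to change.** State in SAP 10 that the 95% interval for incidence differences is the Miettinen-Nurminen score interval, RISKDIFF(CL=MN), and that it also applies to fixed rows with no events in either arm. Confirm that the SAS release used supports the option, since SAP 6.1 sets only a minimum version. Make the change before the blind is broken. If the mock-ups already name a type, put that type in SAP 10 so the two documents agree.

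The cost is one sentence and one code option. Rare-event intervals widen: 1 v 0 from 1.30 to 2.80 points, 3 v 0 from 2.25 to 3.17. MN is slightly conservative overall (two-sided coverage 95.6-97.1% on the same grid), with lower-limit misses of 2.7-3.0%, just above nominal. Newcombe would also remove the zero-width rows, but is more conservative than needed (98.0-99.4%). No efficacy conclusion or decision rule changes.
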